Therefore, high omega 3 Camelina oil offers a sustainable, cost-efficient source of EPA+DHA. Compared with the current major source of EPA+DHA (fish oil), it avoids issues of contamination with marine pollutants and pressure on fish stocks. Finally it offers the possibility of being more efficacious compared with fish oils due to the way it carries the EPA+DHA.

This study will measure the effectiveness of high omega 3 Camelina oil compared with equivalent fish oil (similar EPA+DHA content) to:

- Increase the body EPA+DHA status in the short and longer term.
- Exert anti-inflammatory and immunomodulatory influences.

8. Aims & Objectives

The overall aim is to test whether the efficacy of dietary high omega 3 Camelina oil is comparable with fish oil for the following:

- The magnitude of the increase and turnover of EPA+DHA in plasma lipids following acute consumption (postprandial period).
- The magnitude of the increase in EPA+DHA derived in plasma lipids and blood cells following consumption over a longer period (provided as a dietary supplement for 8 weeks).
- In vivo and ex vivo anti-inflammatory effects following acute and longer duration consumption.

Objectives

- To measure the appearance of EPA and DHA in individual blood lipid classes (phospholipids, triacylglycerol (TAG), non-esterified fatty acids (NEFA) and cholesteryl esters (CE)) and specific lipoprotein fractions (chylomicrons and very low density lipoprotein) and blood cells (erythrocytes and peripheral blood mononuclear cells) in the blood of healthy subjects over 8 hours following consumption of a standard high fat meal containing high omega 3 Camelina oil compared with consuming the same meal containing an equivalent fish oil (similar EPA+DHA content). (Study A)
- To measure the appearance of inflammatory mediators (including CCL2/MCP-1, CCL4/MIP-1 beta, CRP, IL-1beta, IL-6, IL-8, IL-10, IL-12p70, sICAM-1, Serpin E1/PAI-1, sVCAM-1, TNF-alpha and VEGF and CRP) in the blood of healthy subjects over 8 hours following consumption of a standard high fat meal containing high omega 3 Camelina oil compared with consuming the same meal containing an equivalent fish oil (similar EPA+DHA content). (Study A).

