3. To measure the concentration of EPA and DHA in individual blood lipid classes (phospholipids, triacylglycerol (TAG), non-esterified fatty acids (NEFA) and cholesteryl esters (CE)) and blood cells (erythrocytes and peripheral blood mononuclear cells) in the blood of fasted healthy subjects following consumption of high omega 3 Camelina oil for 8 weeks compared with consuming an equivalent fish oil (similar EPA+DHA content) for the same time period. (Study B).
4. To measure in vitro immune responses (mononuclear cell mediator production, mononuclear cell and neutrophil phagocytosis and respiratory burst response, T cell signalling) by cells from the blood of fasted healthy subjects following consumption of high omega 3 Camelina oil for 8 weeks compared with consuming an equivalent fish oil (similar EPA+DHA content) for the same time period. (Study B).

9. The study

Subjects

For each study (A and B) we will recruit to enrol 10 healthy men and 10 healthy women each in two age ranges (18 to 30 years or 50 to 65 years). We estimate (based on past experience) that this will require screening of approximately 30 men and 30 women in each age group for each study⁵⁵.

For the purpose of this study healthy will be defined as having health screening results that are within normal ranges, a body mass index of 18.5-30.0 kg/m² and without diagnosis of chronic illness.

Inclusion criteria

1. Male or female
2. 18 to 30 years or 50 to 65 years
3. Body mass index 18.5-30.0 kg/m²
4. Health screening results that are within normal clinical ranges (systolic blood pressure ≤ 140 mm/Hg, diastolic blood pressure ≤ 90 mm/Hg, total cholesterol concentration < 7.5 mmol/L, random glucose concentration < 11 mmol/L)
5. Not consuming fish oil or other oil supplements
6. Not eating more than one oily fish meal per week
7. Willing to adhere to the study protocol
8. Being able to provide written informed consent

Exclusion criteria

1. Aged < 18 years; 31-49 years or > 65 years
2. Body mass index < 18.5 or > 30 kg/m²
3. Current smoker
4. Random sample blood cholesterol or glucose concentrations outside the normal concentration range
5. Diagnosed chronic illness (for example diagnosed cardiovascular disease, diabetes, cancer, rheumatoid arthritis)
6. Diagnosed food allergy.
7. Regular use of anti-inflammatory medication (e.g. aspirin, ibuprofen, diclofenac) or anti-coagulant therapy.

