- All data will be entered on a password-protected computer. This data will be accessed only by the PI and the researchers involved.
- All data will only be linked to study codes and thus not identifiable with the source volunteer. However, the caveat to this will be a data set recording the volunteer name and study code without any other volunteer details.
- All data recorded on paper will be kept in a locked filing cabinet in the researchers' office and/or in a dedicated, restricted access, clinical data storage area on Level D of the IDS Building, University of Southampton.
- Data of an identifiable nature (i.e. volunteer names, contact details, addresses) will be destroyed 12 months after the end of the study. All other data will be kept securely for 15 years and then destroyed.
- Data will be obtained, handled and stored in adherence to the principle set out in the Data Protection Act 1998.
- The investigators will permit monitoring, audits, REC and MHRA review (as applicable) and provide direct access to source data and documents.

11. Statistical Analysis

The statistical analysis will involve the comparison of inflammatory markers (proteins, lipids etc) and of fatty acids between fish oil and High omega 3 Camelina oil supplements. All statistical comparisons will be performed at the end of the study using SPSS version 21 (or later).

12. Sample size calculation

Study A. Based on our published findings¹⁶, ten subjects per group will provide 85% power for detecting a 10% difference in peak postprandial concentrations of EPA or DHA in plasma TAG at $\alpha = 5\%$ and $\beta = 7.5\%$ in a two tailed analysis. Based on our previous findings of the effect of consuming a FO-enriched meal on lipoprotein size and concentration¹⁷, Ten subjects per group will provide 85% power for detecting 13 nmol/l difference in peak postprandial VLDL concentration and 11 nm difference in VLDL particle size ($\alpha = 5\%$ and $\beta = 7.5\%$) in a two tailed analysis. Based on our preliminary data, ten subjects per group will provide 80% power for detecting a maximum change of 0.8pg/ml IL-6 (30% difference) in a two-tailed test ($\alpha = 5\%$ and $\beta = 20\%$).

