Study B. Based upon our previous work¹⁸, ten subjects per group will provide 80% power for detecting a 40% increase in EPA or DHA in plasma phospholipids ($\alpha = 5\%$ and $\beta = 7.5\%$) in a two tailed test based upon after 30 days supplementation. Based upon our previous work¹⁹, ten subjects per group will provide 85% power for detecting a 10% increase in concanavalin A stimulated IL-4 and IL-2 secretion in vitro ($\alpha = 5\%$ and $\beta = 7.5\%$) in a two tailed test based upon after 30 days supplementation. In the first instance, data from the two phases of the cross over studies will be compared for time effects and if no significant time effects are detected, the data sets for each treatment will be combined¹⁸. Non-parametric data will be normalised by log transformation. The postprandial changes in plasma metabolites will be analysed by ANOVA with treatment, age and sex as fixed factors and time as a repeated measure. The effect of the different oils on plasma metabolites and immune function in the dietary supplementation study will be assessed by ANCOVA with baseline as a covariate.

13. Safety assessments

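### Section 12 pairs 80% and 85% power with a beta of 7.5%, and gives no 8-week oil-versus-oil detectable difference for Study B's 40-person crossover

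*Combined protocol and SAP*

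**What the plan says.** Section 12 makes two power statements for Study B:

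- Fatty acids: "ten subjects per group will provide 80% power for detecting a 40% increase in EPA or DHA in plasma phospholipids", with alpha 5% and beta 7.5%.
- Immune function: "ten subjects per group will provide 85% power for detecting a 10% increase in concanavalin A stimulated IL-4 and IL-2 secretion in vitro", with the same alpha and beta.

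Both are qualified as "in a two tailed test based upon after 30 days supplementation".

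Section 12 makes three statements for Study A. Those for plasma TAG EPA/DHA and for VLDL each print 85% power with beta 7.5%. The IL-6 statement prints 80% with beta 20%.

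The comparison to be made is described elsewhere. Section 8 aims to "test whether the efficacy of dietary high omega 3 Camelina oil is comparable with fish oil", and objectives 3 and 4 place the Study B comparison after 8 weeks of each oil. Section 9 enrols 10 men and 10 women in each of two age ranges. Each person takes both oils for 8 weeks, with a 6-week wash-out between, at 450 mg EPA plus DHA per day from either oil. Section 11 plans a "comparison of inflammatory markers (proteins, lipids etc) and of fatty acids between fish oil and High omega 3 Camelina oil supplements". Section 12 adds that "if no significant time effects are detected, the data sets for each treatment will be combined", and that "The effect of the different oils on plasma metabolites and immune function in the dietary supplementation study will be assessed by ANCOVA" with baseline as covariate. The Sample analysis part of section 9 also plans a repeated-measures comparison across time as well as between groups.

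**The concern.** There are two problems.

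First, beta is the type II error rate, so power is 1 minus beta. Four of the five power statements in section 12 break that identity. This needs no interpretation: in each of the four, at least one printed figure is wrong.

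Second, the Study B statements do not line up, as worded, with the oil comparison. They speak of an increase where the comparison is a difference between two oils matched on EPA plus DHA. They use ten per group where 40 people serve as their own controls, and 30 days where the plan has 8 weeks. No SD, coefficient of variation or within-person correlation is stated, so a reader cannot convert one into the other.

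The aim is comparability, so a finding of no difference will be used as evidence. Its weight depends on how large a difference the study could have missed, and the plan does not say.

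**Working it through.** **1. Power against beta.** Power = 1 − beta.

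| Statement (section 12) | Printed power | Printed beta | 1 − beta |
|---|---|---|---|
| A: TAG EPA/DHA | 85% | 7.5% | 92.5% |
| A: VLDL | 85% | 7.5% | 92.5% |
| A: IL-6 | 80% | 20% | 80% |
| B: phospholipid EPA/DHA | 80% | 7.5% | 92.5% |
| B: IL-4, IL-2 | 85% | 7.5% | 92.5% |

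Only the IL-6 line is consistent.

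**2. Planned n.** (10 men + 10 women) × 2 age ranges = 40 for Study B. The total is not printed.

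**3. Reproducing ten per group.** This cannot be done, because no SD is stated. What can be done is to find the SD that the printed figures imply. I used the noncentral t, two-sided 5%, n = 10. The noncentrality is d√10 for a paired test (9 df) and d√(10/2) for two groups (18 df). SD = effect / d. Each was solved at the printed power and at 92.5%.

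| Reading | EPA/DHA: d | SD = 40/d | IL-2/IL-4: d | SD = 10/d |
|---|---|---|---|---|
| Paired, printed power | 0.996 | 40.2 | 1.066 | 9.4 |
| Paired, 92.5% | 1.212 | 33.0 | 1.212 | 8.3 |
| Two-sample, printed power | 1.325 | 30.2 | 1.417 | 7.1 |
| Two-sample, 92.5% | 1.609 | 24.9 | 1.609 | 6.2 |

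**4. The planned crossover.** With n = 40 paired (39 df), 80% power needs a difference of 0.454 SDs of the within-person difference. That SD is SD × √(2(1 − ρ)), where ρ is the correlation between a person's responses to the two oils. Assumptions: the SDs from step 3 hold at 8 weeks, all 40 complete, and ρ lies between 0 and 0.9. Detectable difference = 0.454 × SD × √(2(1 − ρ)), in percentage points:

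| Reading | EPA/DHA: ρ = 0 | 0.5 | 0.9 | IL-2/IL-4: ρ = 0 | 0.5 | 0.9 |
|---|---|---|---|---|---|---|
| Paired, printed power | 25.8 | 18.2 | 8.2 | 6.0 | 4.3 | 1.9 |
| Paired, 92.5% | 21.2 | 15.0 | 6.7 | 5.3 | 3.7 | 1.7 |
| Two-sample, printed power | 19.4 | 13.7 | 6.1 | 4.5 | 3.2 | 1.4 |
| Two-sample, 92.5% | 16.0 | 11.3 | 5.1 | 4.0 | 2.8 | 1.3 |

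Example: 0.454 × 40.2 × √2 = 25.8.

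**5. The plan's own effect sizes read as differences between oils.** Take the least favourable case, the largest SD with ρ = 0. For EPA/DHA, 40 / (40.2 × √2) = 0.70 SDs, and power at n = 40 is 99.1%. For IL-2/IL-4, 10 / (9.4 × √2) = 0.75 SDs, and power is 99.6%. Every other combination is higher.

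**6. Dropout.** Section 13 anticipates withdrawals, but no allowance is stated. If 32 complete (an assumption), the multiplier becomes 0.511 and the upper end for EPA/DHA rises from 25.8 to 0.511 × 40.2 × √2 = 29.0 points.

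**The case against.** The strongest reply is that the wording is ambiguous, not wrong. Ten per group is two-group language, and Study A uses it with the word difference. Study A's IL-6 line equates a change with a percentage difference, so the word increase does not settle which contrast was meant. The 30-day phrase may describe only the source data. Ten may be one age-by-sex cell, since each cell has exactly ten people. A comparison across time is planned too, so a power statement for a rise matches something in the plan. All of this stands. A reader might infer that the printed figures certainly do not concern the oil comparison; the documents do not prove that. But none of these readings supplies an 8-week between-oil detectable difference for the crossover.

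It can also be said that nothing in the design changes, and that step 4 rests on choices the plan does not make: the range of ρ, full completion, and an SD carried from 30 days to 8 weeks. That also stands, so those figures are an illustration. Reported confidence intervals would help afterwards. Restating power would not say how large a difference still counts as comparable; the plan gives no margin, and that is a separate question.

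None of this touches the power/beta contradiction. A guess that 7.5% was meant per tail would give 100 − 2 × 7.5 = 85%, but beta is not split in that way and the guess would not explain the 80%.

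**Conclusion.** The concern holds in two parts. The power/beta contradiction is certain: four of the five statements in section 12, two in each study, print a power that differs from 1 − beta by 7.5 or 12.5 percentage points. The documents do not show which figure was intended.

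The second part is a gap in documentation. Section 12 gives no 8-week oil-versus-oil detectable difference for Study B under any reading. Under the assumptions in the working, that difference could lie anywhere from about 5 to 26 points for EPA/DHA and from about 1.3 to 6 points for IL-2/IL-4. The plan gives a reader nothing with which to narrow those ranges.

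A reader might infer that Study B is too small. The documents do not support that. For the same effect, 40 people as their own controls carry more information than ten per group, and power for the plan's own 40% and 10% effects as between-oil differences is about 99% or more even with no within-person correlation. The correction is worth making, but it is no reason to change the design.

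**What to change.** In section 12:

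- Correct the power/beta pairs in both studies so that each statement carries one consistent power.
- Say what ten per group means, in particular whether it is one age-by-sex cell.
- Restate Study B's power as the 8-week difference between oils detectable with the total crossover n, allowing for dropout. Give the SD from the cited earlier work and the within-person correlation assumed. Two entries in the reference list are numbered 18, so say which one supplies the SD for the fatty-acid statement.

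Sample size and planned analyses stay as they are. The cost is a recalculation and some rewording, and the restated figures may look less favourable than the printed ones.

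### Four of the five power statements in section 12 contradict themselves: a type II error of 7.5% (92.5% power) is printed beside 85% power three times and 80% power once

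*Combined protocol and SAP*

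**What the plan says.** Section 12 (Sample size calculation) contains five power statements. All refer to ten subjects per group, α = 5% and a two-tailed test. Some quotes below break off just before the percent sign that follows the value of β.

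- **Study A, plasma TAG:** "ten subjects per group will provide 85% power for detecting a 10% difference in peak postprandial concentrations of EPA or DHA in plasma TAG", and then "in plasma TAG at $\alpha = 5\%$ and $\beta = 7.5\%$ in a two tailed analysis".
- **Study A, VLDL:** "Ten subjects per group will provide 85% power for detecting 13 nmol/l difference in peak postprandial VLDL concentration"; the same sentence adds particle size and the error rates: "13 nmol/l difference in peak postprandial VLDL concentration and 11 nm difference in VLDL particle size ($\alpha = 5\%$ and $\beta = 7.5".
- **Study A, IL-6:** "80% power for detecting a maximum change of 0.8pg/ml IL-6 (30% difference) in a two-tailed test ($\alpha = 5\%$ and $\beta = 20".
- **Study B, plasma phospholipids:** "80% power for detecting a 40% increase in EPA or DHA in plasma phospholipids ($\alpha = 5\%$ and $\beta = 7.5".
- **Study B, IL-4 and IL-2 secretion:** "85% power for detecting a 10% increase in concanavalin A stimulated IL-4 and IL-2 secretion in vitro ($\alpha = 5\%$ and $\beta = 7.5".

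β is not defined in any other sense, and no SD accompanies any of the five. For enrolment, section 9 (Subjects) says of each study that "we will recruit to enrol 10 healthy men and 10 healthy women each in two age ranges". That is 2 sexes × 2 age ranges × 10 = 40 subjects per study, and each subject receives both oils.

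**The concern.** Power and β are complements, so each statement gives the same quantity twice and the two must agree. In four of the five they do not. A reader cannot tell whether the planned risk of missing the stated effect with ten subjects is 7.5% or 15% (three statements), or 7.5% or 20% (the phospholipid statement). With no SD or named test, the reader cannot recompute the answer either.

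Section 12 is the only sample size justification in the documents. What is at stake is whether its stated figures can be relied on, and whether anyone can later say what the study was designed to detect with ten subjects.

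**Working it through.** **Inputs.** Printed power and β for each statement, section 12.

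**Step 1. Power = 1 − β.**

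| Statement | Printed power | Printed β | 1 − β | Gap (points) |
|---|---|---|---|---|
| A: IL-6 | 80% | 20% | 80% | 0 |
| A: plasma TAG EPA/DHA | 85% | 7.5% | 92.5% | 7.5 |
| A: VLDL concentration and size | 85% | 7.5% | 92.5% | 7.5 |
| B: IL-4/IL-2 | 85% | 7.5% | 92.5% | 7.5 |
| B: phospholipid EPA/DHA | 80% | 7.5% | 92.5% | 12.5 |

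The IL-6 line reproduces, so the section itself uses β in the ordinary sense. The other four lines do not. The VLDL statement covers two endpoints and is counted once.

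**Step 2. Size of the disagreement in type II error.** For the 85% lines, (1 − 0.85)/0.075 = 0.15/0.075 = 2.0. For the phospholipid line, (1 − 0.80)/0.075 = 0.20/0.075 = 2.67.

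**Step 3. Is there a convention that reconciles them?**

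- *β halved, as one halves a two-sided α.* 15%/2 = 7.5% fits the three 85% lines. The phospholipid line would then need 20%/2 = 10%, but it prints 7.5%. The IL-6 line would also need 10%, but it prints 20%.
- *Power quoted two-sided, β one-sided.* By normal approximation, an effect with 85% two-sided power at n = 10 has 91.2% one-sided power, close to 92.5%. An effect with 80% two-sided power has 87.6%, which is not close. All five lines say two-tailed.

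Neither reading covers all five lines, and neither explains the phospholipid line.

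**Step 4. What the gap means at n = 10.** The ten cannot be reproduced from the stated effects, because no SD is given. The standardised effect d that ten subjects imply can be found from the non-central t distribution, two-sided 5%. The two-sample test has df = 2n − 2 and non-centrality d√(n/2); the paired test has df = n − 1 and non-centrality d√n.

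| Power | d, two-sample (10 per group) | d, paired (10 subjects) |
|---|---|---|
| 80% | 1.325 | 0.996 |
| 85% | 1.417 | 1.066 |
| 92.5% | 1.609 | 1.212 |

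The ratio of 92.5% to 85% is 1.135 (two-sample) or 1.136 (paired). The ratio of 92.5% to 80% is 1.214 or 1.217.

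If the printed power is right, the effect detectable with β = 7.5% is larger than stated:

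- 85% lines: 10% × 1.135 ≈ 11.4%; VLDL 13 × 1.135 ≈ 14.8 nmol/l and 11 × 1.135 ≈ 12.5 nm.
- Phospholipid line: 40% × 1.214 to 1.217 = 48.6% to 48.7%.

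If β is right, the effect detectable at the printed power is smaller: 10%/1.135 ≈ 8.8% and 40%/1.214 ≈ 32.9%.

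These percentages assume that effects scale linearly. On a log scale, which section 12 allows for some data, the phospholipid figures become 1.40^1.214 to 1.40^1.217, an increase of 50.5% to 50.6%, and 1.40^(1/1.214), an increase of 31.9%. The 10% lines barely move (1.10^1.135 gives 11.4%).

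**Step 5. The same gap in subjects.** By normal approximation for two independent groups at a fixed effect and SD, the n for 92.5% power is 1.287 times that for 85% and 1.472 times that for 80%. If ten gives 85%, 92.5% needs 12.87, so 13 per group. If ten gives 80%, it needs 14.7, so 15.

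**Step 6. Does it matter for the whole study?** Take the d values that give 80 / 85 / 92.5% power at n = 10. At n = 20, power is 98.8 / 99.5 / 99.9% (paired) or 98.3 / 99.2 / 99.9% (two-sample). At n = 40 it exceeds 99.99% in every case.

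**The case against.** The case on the other side accepts the contradiction and disputes its weight.

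- **It changes nothing in the conduct of the trial.** No endpoint, analysis or enrolment number is shown to depend on it. This stands, and it is why the conclusion is confined to the stated figures.
- **Three of the four pairs have a likely explanation.** 7.5% is half of 15%, so 85% power was probably intended and β mislabelled. The lines draw on different sources, so conventions might differ between them. This is plausible, but it does not make the printed β correct, it is not stated anywhere, and it leaves the phospholipid pair unexplained.
- **The detectable-effect conversions look more precise than they are.** This stands for the phospholipid line: the choice of scale (48.6% or 50.5%) matters more than the choice between paired and two-sample tests. The conversions illustrate size only.
- **The meaning of a group of ten is inferred.** Section 12 does not define it; section 9 suggests one age-by-sex cell. The Study B phospholipid line is also worded as a rise after supplementation, so it may be a change from baseline and not a contrast between oils. The figures for 20 and 40 subjects may then not apply to it. This stands as a caveat on step 6 and does not affect steps 1 to 3.
- **Asking for SDs and tests goes beyond the contradiction.** The missing SDs are a separate gap that affects the IL-6 line too. They are still what a reader needs to confirm which figure of each pair is right.

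**Conclusion.** The concern holds. Four of the five power statements in section 12 are wrong as written: in each, the power or β, or possibly both, is incorrect, and the documents do not show which. The stated type II error differs from the one implied by the stated power by 7.5 percentage points in three statements and 12.5 in one. This rests only on power = 1 − β, which is how the IL-6 statement in the same section uses it.

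The consequence is limited. The inconsistency does not show that the trial is underpowered and does not support a change in enrolment. If ten is one age-by-sex cell and the same standardised effect carries over to the pooled comparison of oils, neither of which the documents establish, the choice between the figures makes no practical difference with 40 subjects. It then matters only for claims about ten. It is still worth correcting, because this is the trial's only sample size justification.

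**What to change.** Retrieve the original calculations for the TAG, VLDL, phospholipid and IL-4/IL-2 lines, and re-run them from the source SDs. Restate each line with a single power and β = 1 − power. Beside each, give the SD, the test (paired or two-sample, and the scale) and what the ten subjects refer to, so that the figure can be checked.

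The cost is one corrected paragraph in section 12. A stated power or β may turn out less favourable than printed. The correction adds no burden for participants.

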The high omega 3 Camelina oil contains around 10% of fatty acids as EPA and 10% as DHA. It will be given incorporated into the high fat meal for study A and as dietary supplement oil for study B. Subjects will be randomised to allocate order of supplement. Subjects, researchers and clinical staff will be blinded to group allocation.

Subject participation schedule

Study A

Subjects who express an interest will be contacted by telephone or email. If they fit the inclusion and exclusion criteria they will be sent the information sheet. They will be contacted about 7 days later to confirm their interest or not. If they remain interested an appointment will be made for them to visit the NIHR Wellcome Trust Clinical Research Facility, Southampton General Hospital. At this first visit the study will be explained, any questions answered and written consent obtained; subjects will then have height, weight, and blood pressure measured and a screening blood sample collected (10 ml) to confirm that they meet the inclusion criteria. An appointment will be made for the subsequent clinic visit; one further clinic visit will be made (i.e. three clinic visits in total). Subjects will attend the 2 latter clinic visits in the fasted state (no food or drink except water after 8 pm the previous evening).

Subjects will visit the Wellcome Trust Clinical Research Facility, Southampton General Hospital on three occasions.

[figure not shown]
At the second and third visits the subjects will attend the clinic between 7 and 9 am and will have a cannula inserted into a forearm vein and a baseline blood sample (10 ml) collected. Subjects will then consume one of the test meals on each of two study visits in random order.

The composition of the test meals will be based upon typical UK nutrient intakes as we have used in previous post-prandial studies. The lipid component will be derived from a blend of fat sources (fish oil or high omega 3 Camelina oil, safflower oil, double cream, linseed oil and olive oil) to model the fatty acid profile of the UK diet. Approximately 450 mg EPA plus DHA will be provided by the oils (fish oil or high omega 3 Camelina oil) for the meal challenge (providing the recommended UK daily intake)¹⁷.

Blood samples (10 ml) will then be collected for 8 hours (at 30 minute intervals up to 3 hours and then hourly; total volume sampled 120 ml). A light meal (e.g. sandwiches) will be provided at the end of

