Visits 1 and 2 and 3 to 4 will be around 8 weeks apart and subjects will consume fish oil or high omega 3 Camelina oil daily during that period. Visits 2 to 3 will be a 6 week wash-out period.

Activity	Screening Visit	Study Visit 1	Study Visit 2	Study Visit 3	Study Visit 4
Subject fasted		X	X	X	X
Informed consent	X				
Height	X				
Weight	X	X	X	X	X
Blood for screening	X				
Blood for fatty acids, and in vitro immune and inflammatory responses		X	X	X	X

Sample analysis

Blood collected at study entry will be used for screening. This will be analysed by the University Hospital Southampton NHS Foundation Trust Chemical Pathology Laboratory for blood cholesterol and blood glucose.

Study A. At the 2 study visits blood will be used to prepare plasma, mononuclear cells and red cells. Plasma will be aliquoted and frozen at minus 80°C. Mononuclear cells and red cells will be frozen at minus 80°C. Lipid will be extracted from plasma and red cells using chloroform/methanol and fatty

acid composition determined using standard techniques. Size distribution and concentration of chylomicron, VLDL, LDL and HDL lipoprotein particles will be analysed by NMR in samples collected at baseline, 3 and 8 hours. Immune and inflammatory mediators will be measured in plasma using multiplex immunoassays.

Study B. At the 4 study visits blood will be used to prepare plasma, mononuclear cells and red cells. Plasma will be aliquoted and frozen at minus 80°C. Mononuclear cells and red cells will be frozen at minus 80°C. Lipid will be extracted from plasma and red cells using chloroform/methanol and fatty acid composition determined using standard techniques.

Plasma will be used to evaluate blood lipid concentration and particle sizes

Mononuclear cells will be cultured for 24-48 hours and immune mediators in response to stimulation measured in plasma will be measured using multiplex immunoassays and ELISA.

Whole blood will be used to investigate neutrophil phagocytosis and respiratory burst response to bacterial challenge. Whole blood will be used to measure mononuclear cell phagocytosis.

T cells from the mononuclear cells will be mitogen stimulated and the RNA harvested in prepared for microarray analysis of the T cell transcription.

Data will be compared across time and between groups by ANOVA with repeated measures.

10. Data handling and record keeping

- All data will be entered onto a spreadsheet (Microsoft Excel) by the researchers involved.

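### Study A: the postprandial model does not use the pre-meal value from each visit as a covariate and leaves its role undefined; adjusting for it is a cheap improvement of uncertain size

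*Combined protocol and SAP*

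**What the plan says.** Study A is a two-period crossover (Section 9, Study A): "Subjects will then consume one of the test meals on each of two study visits in random order". At both test-meal visits subjects "will have a cannula inserted into a forearm vein and a baseline blood sample (10 ml) collected" before eating. Sampling then runs for 8 hours, "at 30 minute intervals up to 3 hours and then hourly; total volume sampled 120 ml".

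The analysis text is at the end of Section 12, under the sample size calculation. For Study A it reads "The postprandial changes in plasma metabolites will be analysed by ANOVA", and the full model is "ANOVA with treatment, age and sex as fixed factors and time as a repeated measure". For Study B the oil effect "will be assessed by ANCOVA with baseline as a covariate". Section 9, under sample analysis, adds a general line: "Data will be compared across time and between groups by ANOVA with repeated measures". Section 11 names the comparisons and the software but no model.

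No text gives the pre-meal value a role in the Study A model, and no text explains why the two crossovers are treated differently. The Study A sentence also names no subject or period term. Period is handled only by a preliminary comparison of the two phases, before the data are combined.

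**The concern.** A baseline that has already been collected, and that may predict the outcome, is usually worth adjusting for. Here the response is described only as postprandial changes, which allows three readings: the pre-meal value is subtracted, it is the first level of the time factor, or it is not used. The three can give different intervals for the same oil comparison.

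Section 8 makes the aim one of comparability between the oils. The width of the interval therefore matters, and so does anything that pulls the estimated difference towards zero, because shrinkage favours a finding of comparability. Leaving the choice open also allows it to be made after the results are seen.

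**Working it through.** **What can be reproduced.** Half-hourly samples to 3 hours give 6, and hourly samples from 4 to 8 hours give 5, so there are 11 post-meal samples. The stated 120 ml equals 12 × 10 ml only if the pre-meal sample is counted: (1 + 6 + 5) × 10 = 120. The protocol thus counts the pre-meal sample in the series, which makes the time-level reading plausible without settling it. The Section 12 power figures cannot be reproduced because no SD is stated.

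**Inputs.** n = 40: 10 men and 10 women in each of two age ranges, per study (Section 9, Subjects). n = 10 is the group size in the Section 12 power statements. r is not in the documents; 0 to 0.9 is an assumed range.

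**Formulas.** In a crossover the oil comparison rests on each subject's difference between visits. Let r be the correlation between the pre-meal and post-meal visit differences, and assume equal variances for the two. Variance relative to post-meal values alone is:

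- change from pre-meal: 2 − 2r
- ANCOVA: 1 − r², times about 1 + 1/(n − 4) for estimating the covariate (37/36 = 1.03 at n = 40; 7/6 = 1.17 at n = 10)
- so ANCOVA against change is (1 + r)/2 times the same cost.

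| r | Change vs post-meal only | ANCOVA vs post-meal only, n = 40 | ANCOVA vs change, n = 40 | ANCOVA vs post-meal only, n = 10 |
|---|---|---|---|---|
| 0 | 2.00 | 1.03 | 0.51 | 1.17 |
| 0.3 | 1.40 | 0.94 | 0.67 | 1.06 |
| 0.5 | 1.00 | 0.77 | 0.77 | 0.88 |
| 0.7 | 0.60 | 0.52 | 0.87 | 0.60 |
| 0.9 | 0.20 | 0.20 | 0.98 | 0.22 |

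**Break-even.** Against post-meal values alone, ANCOVA gains once r² exceeds 1/(n − 3): r = √(1/37) = 0.16 at n = 40 and √(1/7) = 0.38 at n = 10. Against change scores it gains while r is below 2 × 36/37 − 1 = 0.95 at n = 40, or 2 × 6/7 − 1 = 0.71 at n = 10.

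**Equal-variance assumption.** If the pre-meal differences have k times the SD of the post-meal differences, change scores have relative variance 1 + k² − 2rk. This exceeds 1 − r² by (k − r)². Before the covariate cost, ANCOVA is therefore never worse than change, but the two tie when k = r.

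**r is not the raw pre/post correlation.** Assume, for illustration, a same-visit pre/post correlation of 0.6, a cross-visit pre/post correlation of 0.5, and pre/pre and post/post correlations of 0.6. Then r = (2 × 0.6 − 2 × 0.5)/(2 − 2 × 0.6) = 0.25. The variance cut before cost is 0.25² = 6%, against 0.6² = 36% in a parallel-group trial.

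**Time 0 as a level.** The oils cannot differ in effect before the meal. With a constant effect at the 11 later times, the main effect averaged over 12 levels is 11/12 of its value, a shrinkage of 1/12 or about 8%. Section 9 limits lipoprotein NMR to baseline, 3 and 8 hours. If the same model is used there, the main effect is 2/3 of its value, a shrinkage of 1/3. A treatment-by-time contrast would avoid this, but Section 12 does not say which term answers the oil question.

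**The case against.** The strongest reply is that the pre-meal value may already be in use. The response is worded as changes, time is a repeated measure, and the blood volume counts the pre-meal sample in the series. That stands: a reader might infer that the pre-meal value is ignored altogether, and the documents do not support this. They show only that it is not named as a covariate. Subtraction and use as a time level do not remove the problem, however, because each carries the cost shown above.

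A second reply is that a crossover already cancels stable differences between subjects, so a visit-specific baseline may add little, and at n = 10 it can cost precision. This also stands. A reader might infer a saving on the parallel-group scale, such as a 25% variance cut at a pre/post correlation of 0.5, equivalent to raising 40 subjects to about 53 (40/0.75). The documents do not support that, because r is not given and a raw pre/post correlation can overstate the gain. Nor can precision be said to be given away for nothing: with r near zero, adjustment loses a little.

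A third reply is that Study B has its own reason to adjust, namely a washout whose completeness is checked by the blood sample at study visit 3, while Study A uses single meals at least 14 days apart, in fasted subjects with limited oily fish intake. That weakens the inconsistency as evidence of error. It does not define the Study A response.

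**Conclusion.** The point holds as a cheap improvement of uncertain size. Study A collects a pre-meal value at each visit, does not name it as a covariate, and leaves its use open. At n = 40 adjustment ranges from about 3% more variance than post-meal values alone (r = 0) to about half the variance (r = 0.7). Against change scores it has lower variance up to r of about 0.95. These figures assume a within-subject analysis, an assumed range for r, the approximate covariate cost and, for the change-score comparison, equal variances of the pre-meal and post-meal differences.

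The shrinkage of 1/12 or 1/3 applies only if time 0 stays in the repeated outcome and the treatment main effect is the target. A reader might infer that leaving out the covariate biases the trial. It does not by itself bias the randomised comparison of post-meal values.

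**What to change.** In Section 12, for Study A:

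- Define the response as the post-meal values and take time 0 out of the repeated outcome.
- Use a within-subject crossover model with subject, period and treatment, keeping age, sex and time, and name the term or contrast that answers the oil comparison.
- Enter the visit-specific pre-meal value as a covariate so that it acts on within-subject differences. If subject is random, so that age and sex main effects can be estimated, also include each subject's mean pre-meal value.
- Otherwise, state why Study A is handled differently from Study B.

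The cost is a few lines of text, best settled before the data are unblinded, with no new samples or visits. The downside is a small loss of precision if r is near zero: about 3% more variance at n = 40, and up to 17% in a subgroup of 10.
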